An adverse event (AE) is any untoward medical occurrence in a participant during participation in the clinical study or with use of the experimental agent being studied. An adverse finding can include a sign, symptom, abnormal assessment (laboratory test value, vital signs, electrocardiogram finding, etc.), or any combination of these. All AEs will be classified using two criteria: 1) severity, and 2) the likelihood that they are attributed to the study intervention. Additionally, regardless of its severity and attribution classifications, an AE may also be considered “serious” (SAE) and/or an “unanticipated problem” (UAP) if it meets certain criteria. These classifications and criteria are explained in depth below. The severity of AEs is based on their impact on the participant. An AE will be termed: 1) Mild: event has minimal impact on the participant, 2) Moderate: the event causes the participant some inconvenience, 3) Severe: event causes a substantial disruption to the participant’s well-being.

AE/SAEs/UAPs will also be categorized according to the likelihood that they are attributed to Tofacitinib, a classification which must be designated by a study doctor. Specifically, AEs will be categorized as: 1) Definitely related: AE is clearly related to the investigational agent, 2) Possibly related: AE may or may not be related to the investigational agent, 3) Not related: AE is clearly not related to the investigational agent.

An AE is considered unexpected if its nature, severity, or frequency is: 1) not listed in the investigator’s brochure, this study protocol, or informed consent form; and 2) not consistent with the expected natural progression of any underlying disease, disorder, or condition the participant has, including their presenting skin condition and DS.

Finally, any AE, regardless of the above classifications, can also be labeled as a serious adverse event (SAE). An SAE is any AE that results in: 1) death, 2) a life-threatening event, 3) inpatient hospitalization or prolongation of existing hospitalization, 4) a persistent or significant disability/incapacity, 5) a congenital anomaly or birth defect, or 6) an important medical event based upon appropriate medical judgment.

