All AEs are recorded from the Baseline visit (Visit 2) when the IP begins through the final follow-up visit 2 weeks after the last Tofacitinib dose, or final visit of the Extension Arm. Additionally, AEs that occur at Screening (Visit 1) that are considered to be directly related to the screening procures will be reported. AEs are documented in terms of a medical diagnosis. When this is not possible, the AE is documented in terms of signs and/or symptoms observed by the study doctor or reported by the participant. AEs are recorded in REDCap and printed copies of the completed REDCap forms are kept in the participant’s source documentation file. AE incidence rates (number of events per 100 patient years) for the study as a whole will be calculated for monthly reports (see *Safety and Adverse Event Reporting* below).

In published studies evaluating Tofacitinib for treatment of rheumatoid arthritis, the incidence rate was as follows for various AEs: 9.4 for SAEs, 2.7 for serious infection, 3.9 for herpes zoster (shingles), 0.3 for opportunistic infection not including tuberculosis, 0.2 for tuberculosis, 0.9 for malignancies, and 0.1 for gastrointestinal perforations. These AE rates are anticipated by this study protocol and have already been deemed safe by the FDA via their approval of Tofacitinib for marketing.

When any AE, regardless of classification, is reported by a participant to any study staff, that personnel will immediately relay the AE information to a study doctor, who will classify the AE appropriately and decide if any follow-up actions should be taken. If needed, follow-up appointments will occur in a timely manner as dictated by the nature of the AE and the discretion of the PIs and study doctors. Similarly, all blood chemistry and laboratory monitoring values will be reviewed as soon as they are available by a study doctor to ensure all results are within normal ranges for a person with Down syndrome or for that specific participant. Abnormal findings will be reported as an AE as appropriate. Detailed information about every AE will be incorporated into a Monthly Progress and Safety Report, as well as Annual Reports, as described below.

Finally, any incident, experience, or outcome may be considered an unanticipated problem (UAP) if it meets the following criteria: 1) it is considered “unexpected” as defined above, 2) it is considered possibly or

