definitely related to the investigational agent, and 3) it suggests that the study places participants at a greater risk of harm (including physical, psychological, economic, or social harm) than was previously recognized. Some AE/SAEs may also be flagged as UAPs, if all three of these criteria are met; however, UAPs can also include study-level events or outcomes encompassing more than one AE or participant.

When any SAE or UAP is discovered by a study coordinator or doctor, that personnel will immediately notify all three study PIs. The contact PI, [name], will be responsible for prompt reporting of any SAE or UAP to the appropriate agents as follows:

- 1) **Fatal or life-threatening SAE:** PIs notify COMIRB, NIAMS, and the DSMB within 48 hours.
- 2) **Possibly or Definitely related to Tofacitinib SAE:** PIs notify COMIRB, NIAMS, and the DSMB within 48 hours.
- 3) **All other SAEs:** PIs notify NIAMS and the DSMB within 48 hours and COMIRB within 5 days.
- 4) **Any UAP:** PIs notify NIAMS and the DSMB within 48 hours and COMIRB within 5 days.

Safety and Adverse Event Reporting.

Monthly Progress and Safety Reports will be compiled by the clinical coordination team for review by the appropriate parties. Progress and Safety Reports will include information regarding recruitment and enrollment status, comparison of targeted to actual enrollment, retention status, and demographic information of participants. These reports will also detail participant adherence to study protocol, which will be evaluated by verbal reports of pill counts at each study visit. Finally, Monthly Progress and Safety Reports will contain summarized AE information including: 1) a list of all AEs reported, including their classifications, actions taken, and outcome 2) a list of all symptoms and their frequency reported by participants, 3) all incidences of laboratory values considered out-of-range for an individual with Down syndrome, 4) a list of all SAEs reported, including their classifications, actions taken, and outcome, and 5) information about any participant deaths, including the cause of death. Monthly Progress and Safety Reports will not include subject- or group-identifiable material. Each report will only include the Study ID.

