The potential risks associated with participation in the study center largely around the usage of Tofacitinib. Increased risks associated with taking Tofacitinib include: development of serious infections and sometimes fatal infections, especially in participants taking concomitant immunosuppressants; development of solid tumor cancer; laboratory abnormalities such as lymphocytosis, neutropenia, anemia, elevated liver enzymes, elevated lipids, elevated serum creatinine, and elevated blood creatine phosphokinase; nasopharyngitis; diarrhea; headache; rash; nausea; and hypertension. Additional risks may include gastrointestinal perforation. These risks will be addressed in the informed consent form.

To mitigate these risks, the design of the inclusion and exclusion criteria, as well as the study visit timeline and safety monitoring labs, have been optimized to meticulously protect participants. Individuals with any active infection and those taking concomitant immunosuppressants will be excluded from the study due to the increased risk of developing severe infections. Individuals with any history of malignant solid tumor cancers will be excluded from the study due to the increased risk of developing a malignancy. Safety monitoring will be performed at each visit to ensure participants do not develop infections or unsafe levels of cell counts, liver enzymes, lipids, creatinine, and creatine phosphokinase. Participants will see a study doctor at each of the eight visits to monitor overall health and ensure any other side effects, such as headache, nausea, diarrhea, or high blood pressure are appropriately managed and reported.

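### Adverse-event severity is graded only by impact on the participant, so a symptom-free laboratory toxicity can be graded Mild at any value, and study doctors may grade it differently

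*Combined protocol and SAP*

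**What the plan says.** Section IV.C, Safety and Adverse Event Monitoring, includes in its definition of an adverse finding an "abnormal assessment (laboratory test value, vital signs, electrocardiogram finding, etc". All AEs are then classified by severity and by attribution. On severity the text says: "The severity of AEs is based on their impact on the participant". It has three levels:

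- "Mild: event has minimal impact on the participant"
- "Moderate: the event causes the participant some inconvenience"
- "Severe: event causes a substantial disruption to the" participant's well-being

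A study doctor classifies each AE. Laboratory results are reviewed to see that they are "within normal ranges for a person with Down syndrome or for that specific participant", and abnormal ones become AEs where appropriate, with no threshold given. Under Safety and Adverse Event Reporting, the monthly report lists AEs with their classifications, actions taken and outcome, and separately lists "all incidences of laboratory values considered out-of-range for an individual with Down syndrome".

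Section V, under Risks, Protections from Risk, and Justifications, names among the risks of tofacitinib "laboratory abnormalities such as lymphocytosis, neutropenia, anemia, elevated liver enzymes, elevated lipids, elevated serum creatinine, and elevated blood creatine phosphokinase".

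**The concern.** All three severity levels describe what the event does to the participant. None refers to a measured value, a multiple of a reference limit or a change from baseline. Such a scale suits headache or nausea. It suits a blood count or a liver enzyme poorly, because a large deviation may cause nothing the participant notices.

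Aim 1 is to define the safety profile of JAK inhibition in Down syndrome. If severity does not follow the value for the kinds of toxicity the protocol most often names, the severity part of that profile says little about them. Severity also has a procedural use. It is one of the features by which an AE is judged unexpected, and being unexpected is one of three conditions for an unanticipated problem, which must be reported to NIAMS and the DSMB within 48 hours.

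**Working it through.** The point rests on the text. The only arithmetic is a count.

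**1. Does the impact scale apply to laboratory findings?** Yes. The AE definition includes abnormal laboratory, vital-sign and ECG findings, and the severity rule covers all AEs without exception.

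**2. Is there another severity scale?** None appears in the supplied text. The places where one might stand give the following:

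| Place | Criterion given |
|---|---|
| Monitoring: when an abnormal value becomes an AE | Where appropriate; no threshold |
| Monitoring: review of results | Range for Down syndrome or for the participant; no ranges stated |
| Reporting: monthly laboratory listing | Out of range for Down syndrome; no grade by value |
| Participant Discontinuation: laboratory criterion | Clinical significance, judged by the study doctor |
| Monitoring: sixth criterion for a serious AE (SAE) | Important medical event, by medical judgment |

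**3. What does the scale do with a symptom-free value?** As an illustration, take two participants with a low neutrophil count at a scheduled draw and no symptoms, one just below the limit and one far below it. If impact means what the participant feels, both are minimal and both are Mild. If one study doctor counts a repeat draw as inconvenience, the second becomes Moderate. If another counts stopping the drug as disruption, it becomes Severe. The text supports each reading, so one value can receive any of three grades.

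**4. How much of the named risk is affected?** Section V names:

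- laboratory: lymphocytosis, neutropenia, anemia, liver enzymes, lipids, creatinine, creatine phosphokinase = 7
- other: serious infection, solid tumor, nasopharyngitis, diarrhea, headache, rash, nausea, hypertension, gastrointestinal perforation = 9

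Total 7 + 9 = 16, and 7/16 = 44%. The next largest grouping is the six clinical effects from nasopharyngitis to hypertension. Laboratory abnormalities are thus the largest group but not a majority.

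**5. Where is the grade used?**

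- In the monthly AE list, which carries each event's classifications.
- In the test for an unexpected event, which looks at nature, severity or frequency. The seven laboratory effects are already listed by nature in the protocol, so for them severity and frequency are the main routes left.
- In the qualitative interim analysis (section VI, Specific Aim 1), which includes all AE data.

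**6. Where is it not used?** The primary safety endpoint allows no more than two SAEs definitely related to treatment. Trial stopping rules 5 and 6 count the same events (more than two within 14.5 patient-years, or later a rate above 13.83 per 100 patient-years). Severity enters none of these.

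**The case against.** The strongest reply is that the grade carries little weight, because the safeguards work without it. A study doctor reviews results as soon as they arrive. Out-of-range values are listed monthly whatever their grade. The AE list shows actions taken, so a discontinuation for neutropenia would be visible even under the label Mild. A clinically significant laboratory finding is an individual stopping criterion, with a repeat within one week. An AE of any severity can be an SAE. No severity tables are specified, and the planned outside comparison is of event rates. All of this stands, and it limits the point.

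It also rules out some stronger readings that a reader might infer:

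- *That symptom-free toxicity must be graded Mild.* The documents do not say so. Impact is not defined as felt symptoms, and a doctor classifies.
- *That a dose-limiting signal could go unseen.* The listings, actions taken and SAE route make that too strong.
- *That the size is 282 panels* (six post-baseline draws × 47 participants). That counts blood draws, not misgraded events. Attrition and the optional post-treatment visit lower it, and extension visits add to it.
- *That the Down syndrome range is wrong as a listing filter.* A population-specific range is defensible, although the ranges should be findable.
- *That participants under-report impact.* The documents give no evidence for this, and a guardian or study partner attends every visit.

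What the reply does not supply is a consistent severity grade. The safeguards rest on individual judgment or unstated ranges. They protect participants one at a time but do not yield a severity profile that can be summarized across them.

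**Conclusion.** The point holds in a limited form. Impact on the participant is the only stated basis for severity, it covers laboratory, vital-sign and ECG findings, and no criterion based on the value is supplied. A symptom-free laboratory toxicity can therefore be graded Mild at any value, and grades may differ between study doctors. This touches the largest group of named risks, 7 of 16. It weakens the classifications in the monthly AE reports, the severity part of the unexpected-event test and the Aim 1 safety profile. It leaves the primary endpoint, the trial stopping rules and the individual safeguards intact. The number of events affected cannot be estimated from the documents.

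The conclusion assumes that no grading scale exists elsewhere. The Data Analysis Plan for Specific Aim 1 refers to a Data and Safety Monitoring Plan that was not supplied. A laboratory scale in that plan would reduce the point to a missing cross-reference. Otherwise the change should be made, though the trial's main safety decision does not depend on it.

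**What to change.** - **Safety and Adverse Event Monitoring:** keep the impact scale for symptoms and clinical events. Grade laboratory, vital-sign and ECG AEs on a published numeric toxicity scale, for example CTCAE, with the version named. If the Data and Safety Monitoring Plan already contains such a scale, cite it instead.
- **Safety and Adverse Event Reporting:** keep the listing against the Down syndrome range, and add each participant's worst grade and shift from their own baseline.

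The change concerns measurement and reporting only, and alters no dose, visit or stopping criterion. It needs protocol wording and a grading field in REDCap. No new samples are needed, since Table 2 already schedules safety panels from screening onward, and values on record can be graded retrospectively so that all participants are treated alike. The price is longer listings, and some events will receive a higher grade because values common in Down syndrome will be flagged. Showing the shift from baseline beside the grade helps the reader interpret those.

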- Males or females with DS between 12 and 50 years of age who weigh at least 40 kg.

- Diagnosis of at least one active immune skin condition, including but not limited to:
 - Moderate-to-severe atopic dermatitis
 - Alopecia areata affecting at least 25% of the scalp
 - Moderate-to-severe hidradenitis suppurativa
 - Moderate-to-severe psoriasis
 - Moderate-to-severe vitiligo.
- Be willing to avoid pregnancy or fathering children.
- Must present with a study partner or legal guardian who can complete, or assist with completing, study materials as appropriate.

Exclusion Criteria

- Weigh less than 40 kg.
- Pregnancy or breast feeding.
- No study partner or legal guardian.
- Vaccination with live attenuated virus within six weeks of inclusion in the study or planned during the study.
- Clinically significant chronic or active viral infection including but not limited to HIV, hepatitis, CMV, EBV, HSV.
- Severe renal impairment.
- History of malignant solid tumor cancer within five years prior to study entry or where there is current evidence of recurrent or metastatic disease.
- Poor venous access not allowing repeated blood tests or non-compliance with venipuncture requirements.
- Prior treatment with a JAK inhibitor or with an investigational agent, device, or procedure within 21 days of enrollment.
- Concomitant treatment with other immunosuppressants (e.g. corticosteroids, methotrexate) or strong CP3A4 or CYP2C19 inhibitors or inducers (e.g. ketoconazole, fluconazole).
- Known allergies, hypersensitivity, or intolerance to Tofacitinib.
- History of thrombotic disorder.
- Superficial skin infection within 2 weeks of inclusion in the study.
- History of disseminated herpes zoster, disseminated herpes simplex, or recurrent localized dermatomal herpes zoster.
- Intravenous antimicrobial therapy within 3 months of inclusion in the study.
- Oral antimicrobials within 2 weeks of inclusion in the study unless on a stable chronic dose and approved by a study doctor.
- Participants may be excluded for other unforeseen reasons at the study doctor's discretion.
- Unable to provide assent in cases where informed consent is obtained from other authorized representative.
- Kidney transplant within the last two years
- Any history of heart attack or stroke.
- Any history of lymphoma.
- Past or current smokers.

C. Study Design and Activities

Recruitment and Pre-Screening.

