Informed consent and assent forms will also be obtained before or at the screening visit. After receiving results from all screening tests and confirming eligibility, a study doctor will prescribe Tofacitinib from the UCHealth or CU Anschutz Medical Center Investigational Pharmacy. We anticipate participants will return for their baseline visit within approximately four weeks of their screening visit. If the duration between Screening and Baseline visit is longer than 4 weeks, study doctors may order screening labs again at their discretion. At the baseline visit, participants will be instructed to begin administration of oral Tofacitinib at 5 mg BID the following morning. Study visits are timed at Time 0 (baseline), 2, 4, 8, 12, and 16-weeks throughout the course of treatment, as well as 2 weeks after ending treatment (18 weeks in total to complete study visits). Participants in the Extension Arm will have an additional visit at 28 weeks with the final follow-up visit at 40-week. Each study visit will occur +/- 3-days of this schedule determined from Time 0 (baseline), except for Extension Arm visits that will occur +/- 7 days of the ideal visit schedule. Missed study visits or visits that occur outside of this window will be reported as a protocol deviation/violation and will not change the original schedule. A missed study visit that was supposed to include dispense of Tofacitinib should be rescheduled, even if outside the allowed window. Study doctors will not continue the Tofacitinib prescription without current safety labs.

Condition	Assessment	Minimum score
Moderate-to-severe atopic dermatitis	Eczema Area and Severity Index (EASI)	≥ 16
Alopecia areata affecting at least 25% of the scalp	Severity of the Alopecia Tool (SALT)	≥ 25
Moderate-to-severe hidradenitis suppurativa	Hidradenitis suppurativa - Physician's Global Assessment (HS-PGA)	≥ 3
Moderate-to-severe Psoriasis	Psoriasis Area and Severity Index (PASI)	≥ 10
Moderate-to-severe Vitiligo	Vitiligo Extent Tensity Index (VETI)	≥ 2

Table 1. Minimum score for inclusion criteria for each skin condition.

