Furthermore, at the end of each study year, the PIs and Clinical Coordination Team will work together to produce an Annual Report. Annual Reports will include (1) a summary of enrollment and retention and participant demographics; (2) a summary of participant adherence to the study protocol; (3) a complete list and overall summary of all AEs; (4) an analysis addressing whether AE rates are consistent with pre-study assumptions; (5) reasons for dropouts from the study; (6) whether all participants met entry criteria; (7) whether continuation of the study is justified on the basis that additional data are needed to accomplish the stated aims of the study; and (8) conditions whereby the study might be terminated prematurely. Annual Reports will not include subject- or group-identifiable material. Each report will only include the Study ID. The Annual Report, and the DSMB report, will also be submitted to COMIRB at the Continuing Review.

Additionally, participants will be notified of UAPs that affect the level of risk of participation, and so result in changes to the protocol or consent, at the time of re-consent for active participants. Participants who have completed active trial participation will be notified in compliance with COMIRB or the NIAMS corrective action plan.

NIAMS will convene a Data Safety and Monitoring Board (DSMB) for this study. DSMB members will have no direct involvement with the study PIs or the investigational agent, Tofacitinib. The DSMB will act in an advisory capacity to NIAMS who monitors participant safety and progress of the study, and review procedures for maintaining data confidentiality, quality, management, and analyses.

Participant Discontinuation and Trial Stopping.

Study doctors, at their discretion, may discontinue Tofacitinib, temporarily or permanently, and/or may remove participants from the study.

Specific trial stopping rules for individual participants are as follows:

- 1) Participant decides to discontinue participation for any reason.

- 2) Participant experiences adverse or allergic reaction to Tofacitinib, as determined by the study doctor.
- 3) Participant experiences an AE that precludes trial completion, as determined by the study doctor.
- 4) Clinically significant abnormal lab finding, as determined by the study doctor. Abnormal lab findings will be repeated within one week to confirm.
- 5) Participant becomes pregnant.

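### A birth defect counts as an SAE, but the adverse-event window normally closes before an exposed pregnancy reaches term, and the protocol gives no procedure for following a pregnancy to outcome

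*Combined protocol and SAP*

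**What the plan says.** All of this is in the combined protocol and SAP.

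- **SAE definition** (IV.C, Safety and Adverse Event Monitoring): criterion 5 of six is "a congenital anomaly or birth defect".
- **AE definition** (same section): "any untoward medical occurrence in a participant during participation in the clinical study or with use of the experimental agent being studied".
- **Recording window** (same section): from Baseline "through the final follow-up visit 2 weeks after the last Tofacitinib dose, or final visit of the Extension Arm". The only other provision is for events caused by screening procedures. There is none for pregnancy.
- **Visit schedule** (IV.C, Study Visits and Activities): 16 weeks of treatment and a visit 2 weeks later, 18 weeks in all. Extension Arm participants have "an additional visit at 28 weeks with the final follow-up visit at 40-week".
- **Pregnancy**: entry requires a participant to "Be willing to avoid pregnancy or fathering children". Table 2 schedules tests at screening, baseline and weeks 4, 8 and 12, with weeks 16 and 28 for the Extension Arm only. Extension Arm participants also test at home in months without a clinic visit. "Participant becomes pregnant" is item 5 of the individual stopping rules (Participant Discontinuation and Trial Stopping).
- **After stopping drug**: item 9 of the same list says that coming off drug need not mean leaving the study.

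**The concern.** The sponsor chose to treat a birth defect as a reportable serious event, and asks both sexes to avoid conception during the trial. A reader would therefore expect a route from a positive test to a recorded outcome. The text covers exclusion, prevention, testing and stopping, and then goes no further. The recording window is tied to the last dose or last visit, whereas this outcome becomes known months later.

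A partner's pregnancy is weaker still. The AE definition concerns an occurrence in a participant, so neither a partner nor a newborn is clearly covered.

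Safety in Down syndrome is Specific Aim 1 and a primary endpoint. If an exposed pregnancy occurred, a final report of no birth defects would not show whether anyone had looked. The prompt notifications to the IRB, NIAMS and the DSMB would depend on someone happening to hear of the event.

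**Working it through.** **The plan's own figure.** 16 weeks of treatment + 2 weeks = 18 weeks, as stated. Visit 7 may be delayed, with treatment to week 18 at most (Visit 7 Considerations). The main-study window can therefore end as late as 18 + 2 = week 20.

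**Assumptions not in the documents.** Term is 37 to 42 gestational weeks, counted from 2 weeks before conception. A pregnancy is found at the first scheduled clinic test at least 2 weeks after conception, drug stops then, and recording closes 2 weeks later.

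**Formulas.** Weeks are counted from baseline.
- Birth week = conception week + gestational weeks − 2, that is, conception week + 35 to + 40.
- Gap = birth week − week the window closes.

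**Main study, window run to its planned end, conception at week 0.** Birth falls at weeks 35 to 40.
- Window to week 18: 35 − 18 = 17, up to 40 − 18 = 22 weeks.
- Window to week 20: 35 − 20 = 15, up to 40 − 20 = 20 weeks.
- Overall range: 15 to 22 weeks.

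**Main study, drug stopped at the next scheduled test.**

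| Conception week | Test week | Window closes | Birth weeks | Gap (weeks) |
|---|---|---|---|---|
| 0 | 4 | 6 | 35–40 | 29–34 |
| 2 | 4 | 6 | 37–42 | 31–36 |
| 6 | 8 | 10 | 41–46 | 31–36 |
| 10 | 12 | 14 | 45–50 | 31–36 |

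These rows give 29 to 36 weeks. A conception just after week 2 misses the week-4 test under the detection assumption and is found at week 8. The shortest gap then approaches 2 + 35 − 10 = 27 weeks. The same holds just after week 6: 6 + 35 − 14 = 27.

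**Extension Arm.** The window runs to week 40, or 41 with the 7-day allowance. The earliest term birth is at conception week + 35. It falls inside only if conception was at or before week 40 − 35 = 5, or 41 − 35 = 6, and only if the participant remained in follow-up despite item 5.

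**Two details that widen the gap.** Main-study participants have no scheduled pregnancy test after week 12, although treatment runs to week 16 (Table 2). Participants living outside the Denver Metro Area may skip the 2-week post-treatment visit (Washout Period).

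**The case against.** A reader might infer that the outcome of an exposed pregnancy can never be recorded, so that this SAE class is empty by construction. The documents do not support that.

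- SAE notification starts when study staff discover the event, with no end date stated.
- Item 9 separates stopping drug from leaving the study.
- Study doctors may arrange follow-up of an adverse event as its nature requires, and extra safety visits during the study.
- An unanticipated problem is defined broadly enough that a partner's pregnancy is not automatically shut out, though its other criteria must be met.
- A pregnancy loss, or an anomaly found before birth, could fall inside the window.
- The Extension Arm window reaches week 40.

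A reader might also pair conception at baseline with detection at week 8 or 12. With birth at week 38 (40 gestational weeks), this gives gaps of 38 − 10 = 28 or 38 − 14 = 24 weeks. That pairing requires the week-4 test to have been missed or falsely negative.

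Nor does a late birth change the formal safety results in any clear way. The primary safety endpoint covers the 16-week period, and trial stopping rules 5 and 6 count only SAEs definitely related to drug.

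Finally, the consent pages were not available for review, and the Data Analysis Plan points to a Data and Safety Monitoring Plan that does not appear under that title. Either may contain pregnancy wording.

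These points rule out any absolute claim, but not the gap itself. Every remaining route relies on discretion or on someone hearing of the event. Nobody is assigned to ask, and no partner procedure exists in the text.

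**Conclusion.** The point holds as a gap in planned safety capture. A defined SAE criterion has no procedure behind it, and the stated window normally closes before term: by about 15 to 22 weeks for a baseline conception with the main-study window run to its planned end, and by about 29 to 36 weeks (27 at the least) when drug is stopped at the next scheduled test. Other plausible definitions of term would move these figures by a few weeks without changing the conclusion.

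Item 5 and item 9 of the individual rules also leave it unclear whether a pregnant participant remains in follow-up.

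The practical weight is modest. The documents do not give the expected number of pregnancies; with 47 participants planned, exclusion at entry and required avoidance, it is very small. No sample size, power or error rate is affected. The conclusion assumes that the consent form and any separate monitoring plan do not already fill the gap.

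**What to change.** Add an exception to the recording window in Safety and Adverse Event Monitoring. A pregnancy in a participant, or with consent in a participant's partner, that was conceived while the participant was on study drug is reported and followed to outcome. Any congenital anomaly is recorded as an SAE and reported through the existing SAE notification route, whatever the time since the last dose.

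Reconcile the recording window with items 5 and 9 of the individual stopping rules, so that the text says whether a pregnant participant stays in follow-up.

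Leave treatment decisions and trial stopping rules 5 and 6 unchanged. Counting late anomalies under those rules would alter what stops the trial, and under rule 6 would add events to a patient-year rate with no matching exposure.

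The cost is the added protocol wording, matching consent text, a few calls for a rare event, and a safety file that may stay open after the participant's last visit.
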